5.4 Blinding and procedures for unblinding the study

5.4.1 Methods for ensuring blinding

This study has a double-blind design with aspirin and matching placebo. The subjects, study site research personnel, academic research center staff, and treating physicians involved in the treatment and/or clinical evaluation of the subjects will not be aware of treatments received. There will be an independent data safety monitoring board (DSMB) to monitor the data on a periodic basis. An independent statistician, not otherwise involved in the study, will prepare and provide the required reports to the DSMB as per the DSMB charter.

5.4.2 Methods for unblinding the study

In the event of a medical emergency, in which knowledge of the investigational drug is critical to the subject's medical management, the blind for that subject may be broken by the treating physician. The investigator should follow the instructions provided in the EDC to obtain the necessary treatment information or call the 24/7 TWILIGHT Medical Monitoring Hotline at [contact]. As the active study drug in this trial is low-dose aspirin, in most instances the subject may be properly managed without the need for unblinding.

5.5 Treatments

5.5.1 Identity of investigational product

In this protocol, the investigational product is enteric coated aspirin (81 mg – 100 mg) tablets and matching aspirin-placebo tablets.

Table 1 Identity of Investigational Product

Investigational product	Dosage form and strength
Aspirin, EC	81 mg – 100 mg tablet, daily
Placebo for aspirin	tablet daily

5.5.2 Doses and treatment regimens

Study-provided medications including open-label ticagrelor at a dose of 90 mg twice daily plus open-label EC aspirin at a dose of 81 mg – 100 mg daily will be dispensed to enrolled participants at the time of discharge and should be taken daily until the in-person 3-month study visit. Study-provided medications including open-label ticagrelor at a dose of 90 mg twice daily plus blinded study drug will be dispensed to randomized participants at the 3-month in-person visit and should be taken daily until end of study.

5.5.3 Additional study drug

Open-label ticagrelor will be administered to all subjects regardless of randomization assignment.

5.5.4 Labeling

Each aspirin/placebo bottle will be labeled in black ink. This label will indicate the protocol number, blinded batch number, container number, blinded drug name, tablet quantity, storage conditions, directions for use and route of administration.

At the study site, the investigational product should be stored in a secure area according to local regulations. It is the responsibility of each site investigator to ensure that the investigational product is only dispensed to study subjects. The investigational product must be dispensed only from official study sites by authorized personnel according to local regulations.

The storage conditions for the subjects to follow will be included in the labeling on the bottles.

5.6 Concomitant and post-study treatment

There are no protocol specific concomitant treatments.

At the End of Study visit physicians caring for the patient will decide which antiplatelet medication the patient should receive as part of his/her ongoing clinical care. This medication(s) will be open label and obtained locally.

5.7 Treatment compliance

Study drug compliance will be assessed using manual pill count at the 9-month and 15-month in-person follow-up visits.

5.7.1 Accountability

Reconciliation between the quantity of shipped study drugs versus the allocation of study drugs via the EDC and versus distribution of study drug to subject will be monitored and reconciled.

5.8 Discontinuation of investigational product or study drug

Study-provided medications (open-label ticagrelor or blinded study drug) may require *temporary interruption* for the following reasons:

- 1. Surgery or invasive procedure:** Study-provided medications should be resumed after surgery once the risk of bleeding is no longer considered prohibitive in the judgment of the treating physician. Minor surgeries and procedures, including but not limited to tooth extraction, colonoscopy and endoscopy, may be safely performed on low-dose aspirin and therefore do not require temporary interruption of blinded study drug. However, if deemed necessary and at the discretion of the treating physician, open-label ASA may be substituted for blinded study drug in the peri-operative period. Blinded study drug may then be restarted at the discretion of the treating physician after completing the mandatory course of open-label ASA.
- 2. Balloon angioplasty or PCI with bare-metal stent:** In the event of coronary revascularization with balloon angioplasty alone or PCI with bare metal stent, blinded study drug may be temporarily interrupted for 2-4 weeks while patients receive open-label ASA at the discretion of the treating physician in accordance with local practice and standard of care. Blinded study drug may then be restarted at the discretion of the treating physician after completing the mandatory course of open-label ASA.
- 3. Clinically Significant Bleeding:** Study-provided medications should be temporarily interrupted pending resolution of the acute bleeding episode and

may be restarted at the discretion of the treating physician if deemed clinically safe and in accordance with local practice and standard of care.

4. Details surrounding the date, duration and reason for each episode of temporary interruption should be entered in the appropriate section of the EDC.

Study-provided medications (open-label ticagrelor or blinded study drug) may require *permanent discontinuation* for the following reasons:

1. Patient decision: The patient is at any time free to discontinue treatment, without prejudice to further treatment.
2. Investigator's decision:
 - a. Incorrectly enrolled patient in whom the inclusion/exclusion criteria violation would put the patient at undue risk
 - b. Adverse Events felt to be related to either study medication for which Investigator feels continued treatment would put the patient at undue risk, such as severe or life-threatening bleeding, myocardial infarction, stent thrombosis, ischemic stroke or coronary revascularization with a DES.
3. Renal failure requiring dialysis
4. Chronic oral anticoagulation
5. Details surrounding the date, duration and reason for permanent discontinuation of study medication should be entered in the appropriate section of the EDC.
6. In the event of permanent discontinuation of either study medication, further antiplatelet therapy is at the discretion of and is to be provided by the patient's treating physician. Any remaining study-provided medication should be returned to the local site at the next scheduled follow-up visit. Although these patients will no longer receive study-related medication, follow-up will continue in all randomized patients until end of study

5.9 Withdrawal from study

Each enrolled subject shall remain in the trial until completion of the required follow-up period. However, a subject's participation in any clinical trial is voluntary and the subject has the right to withdraw at any time without penalty or loss of benefit. Conceivable reasons for discontinuation may include, but not be limited to, the following:

- Subject voluntary withdrawal
- Subject withdrawal by physician as clinically indicated
- Subject lost-to follow-up

The reason for subject discontinuation must be documented in the eCRF and source documents. The individual site Principal Investigators must also report all subject discontinuations to their IRB/EC as defined by their institution's procedure.

All data from evaluations and treatments performed prior to the withdrawal should be documented in the eCRFs. Source documents that pre-date the withdrawal should be submitted as required by the protocol. No data that post-dates the withdrawal will be collected.

Once a subject has withdrawn from the trial, no further follow-up contact will be performed. However, vital status may be obtained from public records. Medical therapy after stopping the study will be as prescribed by the subject's physician.

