7.3.3 Information to be collected for each AE/SAE

- Description of AE/SAE
- The dates when the AE/SAE started and stopped
- Whether the AE/SAE is serious or not
- Investigator causality rating against the investigational product
- Action taken with regard to investigational product
- Whether the AE/SAE caused subject's withdrawal from study
- Outcome

In addition, the following variables will be collected for SAEs:

- Date the study site research personnel became aware of SAE
- Date when decision was made for meeting SAE criteria
- Criteria met leading to classification as SAE
- Date of hospitalization (if applicable)
- Date of discharge (if applicable)
- Date of death (if applicable)
- Probable cause of death (if applicable)
- Autopsy performed (if applicable)

It is important to distinguish between serious and severe AEs. Severity is a measure of intensity whereas seriousness is defined by the criteria in Section 7.2. An AE of severe intensity need not necessarily be considered serious. For example, nausea that persists for several hours may be considered severe nausea, but not an SAE. On the other hand, a stroke that results in only a limited degree of disability may be considered a mild stroke but would be an SAE.

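### Section 5.9 lets a physician take a randomised patient out of the study on clinical grounds and then ends endpoint collection, while Section 5.8 promises follow-up of everyone who stops study drug; the two need reconciling

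*Combined protocol and SAP*

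**What the plan says.** Section 5.9 starts from a sound default: "Each enrolled subject shall remain in the trial until completion of the required follow-up period". It then introduces its list of exits with "Conceivable reasons for discontinuation may include, but not be limited to, the following". The list has three items: the patient's voluntary withdrawal, loss to follow-up, and "Subject withdrawal by physician as clinically indicated". The physician item has no criteria, does not require the patient to have withdrawn consent, and is not confined to the period before randomisation.

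The consequences are stated for every withdrawal alike: "No data that post-dates the withdrawal will be collected" and "Once a subject has withdrawn from the trial, no further follow-up contact will be performed". The only relief is optional and limited to death: "However, vital status may be obtained from public records".

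Section 5.8 deals with permanent discontinuation of study medication. The reasons it names include severe bleeding, myocardial infarction, stent thrombosis, ischemic stroke, dialysis and chronic oral anticoagulation. For patients who stop, item 6 says that "follow-up will continue in all randomized patients until end of study".

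Section 5.3 has its own rule for incorrectly enrolled patients, who are withdrawn at once even if randomised. The physician item in 5.9 is therefore not just the eligibility-error route under another name.

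**The concern.** A well-run trial separates stopping treatment from stopping observation. Section 5.8 does this and 5.9 blurs it. A physician who decides that a patient should come off study drug after a bleed, or because of a new anticoagulation indication, can act under 5.8 (off drug, still followed) or can read 5.9 as allowing removal from the study (no further data). The patient has not refused follow-up, so the missing data are avoidable.

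The trigger for exit is the patient's clinical state, so the missing data are unlikely to be random. A patient removed after a bleed is no longer observed for MI or stroke, and one removed after an ischemic event is no longer observed for bleeding. Section 1.3 itself expects the risks to differ by arm, with more bleeding on aspirin and possibly more thrombotic events on placebo, so exits could differ by arm even under blinding. Section 12.2 gives no sensitivity analysis for informative censoring.

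**Working it through.** **The text, side by side**

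| Question | 5.8 item 6 (drug stopped) | 5.9 (physician withdrawal) |
|---|---|---|
| Consent withdrawn? | Not required | Not required |
| Contact afterwards | Continues to end of study | None |
| Bleeding, MI, stroke collected | Yes | No |
| Death | Yes | Optional, public records |

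The 12.2 censoring rule assigns the last-contact date to patients who withdraw consent or are lost to follow-up. Physician withdrawals are not named, so their handling is open.

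**The plan's own figures**

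Margin: 20% of 8.0% = 1.6 points, as stated. With 8200 randomised and 1:1 allocation (assumed; the text gives no ratio), each arm has 4100 patients, and the margin equals 0.016 × 4100 = 65.6 events.

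Sample size for bleeding: control 4.5%; treated 4.5% × 0.72 = 3.24%; with 4% cross-over in the monotherapy arm, 0.96 × 3.24% + 0.04 × 4.5% = 3.29%. The two-proportion formula (two-sided 0.05, 80% power) gives 8032 in total, and 8032 / 0.98 = 8196, against 8200 stated. The 2% loss allowance (82 per arm) therefore works as an inflation of numbers. It protects precision and does nothing about bias from selective loss.

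**Illustration of size**

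Assumptions: a fraction w = 1% of one arm (41 patients) is withdrawn early and censored; none is withdrawn from the other arm; their later risk q of a counted event is 25% to 50%. Neither w nor q comes from the documents. The arm average P is the plan's 8%.

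Censoring gives withdrawn patients the arm's average risk, so only the excess is lost: net bias ≈ w × (q − P).

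- q = 25%: 0.01 × 0.17 = 0.17 points; 41 × 0.17 ≈ 7 events; 0.17 / 1.6 ≈ 11% of the margin.
- q = 50%: 0.01 × 0.42 = 0.42 points; 41 × 0.42 ≈ 17 events; 0.42 / 1.6 ≈ 26% of the margin.
- q = 8%: zero.

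If these patients were instead carried event-free to day 365, which 12.2 does not exclude, the whole risk is lost: 41 × 0.25 to 41 × 0.50, about 10 to 20 events, or 0.25 to 0.50 points (16% to 31% of the margin).

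**Effect on the non-inferiority error, worst direction**

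Put the truth at the margin (9.6% against 8.0%), with all 41 withdrawals in the monotherapy arm. The observed monotherapy rate is (0.096 − 0.01q) / 0.99. For q = 50% this is 0.0919, an apparent difference of 1.19 points. The nominal one-sided error of 2.5% becomes:

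| q | Error |
|---|---|
| 8% | 2.35% |
| 16% | 3.17% |
| 24% | 4.21% |
| 50% | 9.64% |

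These figures use all randomised patients, not the per-protocol set. If the withdrawals fall in the control arm instead, the bias works against non-inferiority.

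**The case against.** The strongest reply is that 5.8 already covers the obvious examples and promises follow-up of all randomised patients, and that the 5.9 list is only of conceivable reasons: it includes loss to follow-up, which nobody authorises. It also covers patients before randomisation, when a physician's refusal is expected (5.2.1). That makes frequent use of the physician route less likely. It does not remove the route, because 5.8 governs stopping drug and 5.9 governs leaving the study.

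Several stronger readings are tempting, and the documents do not support them.

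- *That both primary endpoints are broadly biased.* Both are times to first event, and 5.9 requires data before withdrawal to be recorded. A patient removed after a qualifying bleed already counts for bleeding, and one removed after an MI or stroke already counts for the ischemic composite. What is lost is mainly the other endpoint, or events after an exit that came before any event.
- *That non-inferiority is favoured.* This needs sicker patients to leave the monotherapy arm in excess. Bleeding-driven exits on aspirin would push the other way. The primary non-inferiority analysis is also per protocol and excludes patients taking less than 80% of dispensed tablets (12.1), so many off-drug patients, even if followed, would contribute only to the secondary intention-to-treat analysis.
- *That these patients will be censored at last contact.* Section 12.2 does not say so.
- *That 7.3.3 shows physician-driven exit is expected.* Its item, "Whether the AE/SAE caused subject's withdrawal from study", can equally record a patient's own decision to leave after an adverse event.

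**Conclusion.** The point holds as an inconsistency between 5.8 and 5.9 that permits avoidable, clinically driven loss of endpoint data. It bears mainly on the intention-to-treat analyses, which are primary for bleeding and secondary for the ischemic endpoint, and less on the per-protocol non-inferiority test. The direction cannot be stated in advance.

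The size cannot be derived from the plan, because no frequency of physician withdrawal is given. The illustrated bias rests on one-sided exits of 1% and on an assumed risk well above average; it shrinks as either assumption is relaxed. A reader might infer that follow-up will stop because patients are doing badly. The wording allows that, but nothing shows that it is intended or would be common. The change is worth making because it is cheap and the loss is preventable.

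**What to change.** In 5.9, add that for randomised patients a physician's decision about study medication, for whatever reason, does not end follow-up or endpoint collection, and that these end early only when the patient withdraws consent to follow-up or is lost to follow-up. Remove or reword the physician item for randomised patients, and close the open-ended lead-in to the list in the same way, since deleting the one item would leave the route open. Cross-refer to 5.3 for incorrectly enrolled patients so that the two sections do not conflict. Apart from 5.3 cases, the remaining early exits are then the ones that 12.2 already names.

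Keep the 7.3.3 item, because it records why a patient left. Nothing here changes when study medication may be stopped.

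The cost is a few sentences in 5.9 and an adjustment to the matching withdrawal option in the eCRF. Visits and calls for patients off drug already exist (5.8 item 6, 6.2.3), so the only downside is a few more patients to follow.

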6. COLLECTION OF STUDY VARIABLES

6.1 Recording of data

The Investigator is responsible for maintaining complete and accurate documentation of the trial including but not limited to medical records, trial progress records, laboratory results, electronic case report forms, signed informed consent forms, investigational product accountability records, correspondence with the IRB or EC as well as trial monitors and sponsor, adverse event reports, and information regarding subject discontinuations.

The Investigator is required to maintain information in the subject's medical records which documents and corroborates data entered in the case report forms. As a minimum the subject record should contain:

- Medical history/physical exam documenting that subject meets inclusion/exclusion criteria
- Documentation of subject's consent and subject ID number in the trial
- Dated and signed notes from each subject visit
- Adverse events reported and their resolution or lack thereof including supporting documents such as hospital records, discharge summaries, catheterization reports, ECGs, etc.
- Record of protocol required medications during the trial
- Record of the subject's condition upon completion of or withdrawal from the trial

6.2 Data collection at enrollment and follow-up

Data collection commences after the subject has provided informed consent and has been enrolled in the study. Data collection, including subject demographic information, laboratory tests, and procedural data as well as follow-up visits or telephone contacts will be conducted

Clinical Study Protocol *TWILIGHT Study*
Drug Substance *Ticagrelor & Aspirin*
Study Number *ISSBRIL0345*
Edition Number *Version 4.0*
Date *28-Mar-2016*

by an Investigator or site coordinator who has been trained on the protocol and electronic Case Report Forms (eCRFs).

Data required for analysis will be obtained as outlined in Table 1. After discharge from the hospital, each enrolled subject will be followed with a phone call at 1 month post enrollment and an in-clinic visit at 3 months post enrollment. Enrolled subjects who do not meet eligibility for randomization *prior to* the in-person 3-month visit will not be required to complete the 3-month in-person visit. Subjects who are randomized at 3 months post enrollment will be followed with a phone call at 4 months post enrollment and will return for additional in-clinic visits at 9 and 15 months post enrollment. A final follow-up phone call will be performed at 18 months post enrollment for randomized subjects. No further follow-up contact will be performed for subjects who did not meet eligibility for randomization at the 3 month visit; however, vital status may be obtained from medical or public records at 18 months post enrollment. A flow chart listing the planned visits and their timing can be found in appendix C).

Table 1 Schedule of Data Collection

Type of Data to be Collected	Enrollment	Post-Procedure or Discharge	1 Month (30d) (±7 days) Phone Call	3 Month (90d) (±14 days) Office Visit	4 Month (120d) (±7 days) Phone Call randomized	9 Month (270d) (± 30 days) Office Visit randomized	15 Month (450d) (± 30 days) Office Visit randomized	18 Month (540d) (± 14 days) Phone Call randomized
Eligibility Criteria	X			X				
Patient Informed Consent	X							
Physical Assessment	X							
Medical History/Risk Factors	X							
Cardiac Status	X							
Medications/Antiplatelets	X							
Clinical Tests* Lab tests, ECG	X			X		X	X	
Procedure Information	X							
DAPT Medication Status		X	X		X			X
Angina Status				X	X	X	X	X
Randomization–if eligible				X				
Dispense medication according to EDC		X		X		X		
Randomized Medications – reconciliation of provided medication						X	X	
Randomized Medications – subject self-reporting of compliance to medications				X	X	X	X	X
Adverse Events / Serious Adverse Events	X	X	X	X	X	X	X	X

*If performed, as per standard of care. Subject may be asked to provide an additional blood sample (10cc) for lipid profile testing if not already performed per standard of care.

6.2.1 Enrollment procedures

After successful PCI with implantation of at least one locally approved drug eluting stent and physician decision to treat subject with low-dose aspirin (81 mg – 100 mg) daily and ticagrelor 90 mg twice daily for 3 months, the investigator or designee will:

- Confirm inclusion/exclusion criteria
- Obtain written informed consent
- Obtain a complete medical history, including lab values for hemoglobin and creatinine as well as an ECG, if performed per standard of care. Subject may be asked to provide an additional blood sample (10cc) for lipid profile testing if not already performed per standard of care.
- Review concomitant medications taken within the last 30 days
- Instruct the subject to notify the investigator of any occurrence of adverse events
- Schedule next clinic visit at 3 months
- Dispense 3- month supply of study medications (open-label ticagrelor and EC aspirin)
- Instruct patients to return all study-provided medication at next in-person clinic visit

6.2.2 In-person follow-up procedure at 3 months

- Assess for adverse events including MI, unstable angina, stroke, and bleeding.
- Review concomitant medications with subject
- Counsel subject about importance of study drug compliance
- Assess for randomization eligibility , if applicable:
 - Randomize subject within EDC and obtain bottle numbers
 - Dispense study medication for next 6 months
 - Schedule next clinic visit at 9 months
- Instruct the subject and/or caregiver to notify the investigator of any occurrence of adverse events
- Instruct patients to return all study-provided medication at next in-person clinic visit

